6.3. Measures to Minimize Bias: Randomization and Blinding

Randomization

Participants who meet all criteria for enrollment will be randomized on Day 1 as follows:

- In Part 1, 1:1 to double-blind treatment
- In Part 2, will be allocated as follows:
 - Prevention Cohort: 1:1:1 to double blinded treatment
 - Treatment Cohort: 1:1, as described in Part 2 Treatment Cohort below
- In Part 3, 1:1 to open label treatment

To achieve between-group comparability, block randomization within each facility will be used. Randomized participants within the facility will be stratified by role within the facility (resident versus facility staff), by sex, and whether or not the participant received a SARS-CoV-2 vaccine prior to screening (in Part 3 only).

All participants will be centrally randomized to study intervention using an Interactive Web Response System (IWRS). Before the study is initiated, the log in information and directions for the IWRS will be provided to each site.

Blinding

Part 1 and Part 2 Prevention Cohort

Part 1 and Part 2 are blinded. Neither participants, nor investigators, nor the sponsor study team will be aware of treatment assignments prior to the final database locks at the conclusion of the study, except as described in the following note.

Note: It is possible that some participants will have the SARS-CoV-2 negative result on the screening point of care test, but could be positive on the baseline SARS-CoV-2 PCR test. The results from the baseline PCR test will not be available until after the participant is randomized. Once positive results are known from the baseline PCR test, these participants will be unblinded and have the option to continue to be followed for safety according to the Prevention Cohort SoA. This table describes general procedures for unblinding.

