9.4.1. General Considerations

Baseline values for all measurements will be the last measurement taking prior to receiving study intervention, unless otherwise specified.

The primary analyses of the primary endpoints and key secondary endpoints will be based on events that occurred after randomization.

The analysis model for time-to-event analyses will be a Cox proportional hazards regression model for the time to the first occurrence of the relevant event, with treatment as a fixed effect. For continuous measures, analysis of covariance (ANCOVA) and/or mixed-effects model for repeated measures (MMRM) will be used to analyze changes from baseline with the baseline

value as the covariate. The MMRM model will include fixed effects for treatment, visit, treatment-by-visit interaction, the baseline as a covariate and the participant as a random effect. Summary statistics will include sample size, mean, standard deviation, median, 10th and 90th percentiles for both the actual and the change from baseline measurements. Least-squares mean (LS mean) and standard error derived from the model will also be displayed for the change from baseline measurement. Treatment comparisons will be displayed showing the treatment difference LS Mean and the 95% confidence limits along with the p-value.

For continuous lab measurements, an analysis of variance (ANOVA) on ranks will be used and p-values for the difference between each study intervention and placebo will be reported.

For categorical measures, summary statistics will include sample size, frequency, and percentage. For primary and secondary analyses, a logistic regression model will be used. The model will include fixed effects for treatment and stratification factors such as facility. For other analyses, frequencies will be analyzed using Chi-square tests if the expected count is at least 5, in at least 80% of the cells, otherwise a Fisher's exact Test will be used.

All analyses will be implemented using SAS[®] Version 9.4 or higher, or R version 3.6.3 or higher.

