**Table PYAD.6.3. Tables and Figures Related to Demographics and Other Characteristics of Study Population**

Method	Analysis
Descriptive Statistics	Number of participants, mean, standard deviation, median, minimum, maximum, and 10 th and 90 th percentiles for continuous measures, and frequency counts and percentages for categorical measures
Kaplan-Meier curves and summary statistics, Cox proportional hazards	Treatment comparisons of time-to-event based endpoints
Logistic regression analysis	Treatment comparisons of binary variables with treatment, facility, and randomization stratification variables in the model

Nonparametric (e.g., Mann-Whitney or van Elteren tests)	Treatment comparison of ordinal, nominal, and non-normally distributed continuous variables
Mixed-effects model repeated measures (MMRM) analysis	Treatment comparisons of continuous efficacy and health outcome variables
Chi-square test or Fisher's exact test	Treatment comparison of binary endpoints

Treatment comparisons of continuous safety variables with multiple postbaseline measurements will be made using MMRM analysis. When MMRM is used, it includes: (a) treatment group, (b) facility, (c) role within the facility (resident vs staff), (d) sex, (e) baseline value in the model, (f) visit, and (g) the interactions of treatment-by-visit as fixed factors, and the patient as a random effect. The covariance structure to model the within-patient errors will be unstructured. If the unstructured covariance matrix results in a lack of convergence, the heterogeneous Toeplitz covariance structure, followed by the heterogeneous autoregressive covariance structure, will be used. The first structure to yield convergence will be used for inference. The Kenward-Roger method will be used to estimate the denominator degrees of freedom. Type III sums of squares for the least-squares (LS) means will be used for the statistical comparison; the 95% confidence interval (CI) will also be reported. Unless otherwise specified, for MMRM, reported data from only planned visits will be used as the primary analysis.

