Treatment comparisons of continuous efficacy and safety variables with a single postbaseline timepoint will be made using analysis of covariance (ANCOVA) with: (a) treatment group, (b) facility, (c) role within the facility (resident vs staff), (d) sex and (e) baseline value in the model. Type III sums of squares for LS means will be used for statistical comparison between treatment groups. The LS mean difference, standard error, p-value-, and 95% CI, unless otherwise specified, will also be reported. Missing data imputation method for the ANCOVA model is specified in Section 6.3.

Treatment comparisons for binary efficacy endpoints will be made using logistic regression. The model will include the treatment groups, facility, and the stratification factors (resident/staff and sex) as explanatory variables. For the primary and key secondary endpoints, p-values from Rao's score test (or score test) will be reported (Rao 1948). For all other endpoints, results from a Wald test will be reported. The odds ratio and the corresponding CIs, as well as the treatment differences and the corresponding CIs, will be reported.

For other binary endpoints, treatment comparisons will be made using Chi-square tests if the expected count is at least 5 in at least 80% of the cells, otherwise a Fisher's exact Test will be used.

The Kaplan-Meier (KM) product limit method will be used for time-to-event analyses. The hazard ratio and log-rank test will be reported. Time for all analyses will be described in units of days.

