## 6.10. Efficacy Analyses

### 6.10.1. Primary Outcome and Methodology

The endpoint for the primary analysis is defined as the first occurrence of COVID-19, defined as the detection of SARS-CoV-2 by reverse transcription – polymerase chain reaction (RT-PCR) AND mild or worse disease severity within 21 days of detection, by Day 57 (8 weeks after randomization).

The percentage of patients in the Prevention population who experience COVID-19 by Day 57 will be summarized by treatment group.

Statistical comparison between each study intervention and placebo will be done using a logistic regression model. The model will include treatment, facility, role within the facility (resident vs staff) and sex as fixed effects. The odds ratio and the corresponding CIs, as well as the treatment differences and the corresponding CIs, will be computed using the Wald method and reported. A p-value from the Rao's score test will be reported.

As an exploratory analysis, the incidence of COVID-19 within 21 days of randomization will be compared across treatment groups in the subset of participants in the Treatment population who are asymptomatic at baseline (as defined in Table 1 of the protocol). Statistical comparisons will use similar methodology as described in Section 6.10.1.

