#### **6.10.2.2. Risk Difference/Time-to-Event Assessment**

The risk difference for COVID-19 between treatments will be estimated by the difference in the percentages of patients in the Prevention population who experience COVID-19 by Day 57, unadjusted for other covariates. A Wald 95% confidence interval for the risk difference will be computed.

The time from randomization to first incidence of COVID-19 will be summarized by treatment for participants within the Prevention population. A 95% confidence interval for the hazard ratio will be computed using a Cox proportional hazards model. Participants who have yet to complete the Evaluation Period at the time of the analysis will be censored at the date of their last visit prior to the analysis.

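### The supplementary Cox model for COVID-19 omits facility, role and sex, so its hazard ratio does not match the randomization or the primary model

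*SAP*

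**What the plan says.** Protocol 6.3 states "To achieve between-group comparability, block randomization within each facility will be used", with stratification inside the facility by role (resident or staff) and sex; vaccine status is added in Part 3 only.

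The models for the primary outcome treat these factors differently:

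- **Primary logistic model (SAP 6.10.1):** "The model will include treatment, facility, role within the facility (resident vs staff) and sex as fixed effects".
- **Mixed-model sensitivity analysis (SAP 6.10.2.1):** keeps the stratification factors as fixed effects and makes facility random.
- **Cox model (SAP 6.10.2.2):** "A 95% confidence interval for the hazard ratio will be computed using a Cox proportional hazards model". No covariate or stratum is named.
- **Protocol 9.4.1, on time-to-event models in general:** "the time to the first occurrence of the relevant event, with treatment as a fixed effect".
- **SAP Table PYAD.6.3:** the logistic row reads "Treatment comparisons of binary variables with treatment, facility, and randomization stratification variables in the model"; the Kaplan-Meier and Cox row reads only "Treatment comparisons of time-to-event based endpoints".
- **SAP 6.1.4, on time-to-event analyses:** "The hazard ratio and log-rank test will be reported", with no mention of stratification.

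The general covariate rule in SAP 6.2 concerns only the baseline value of the endpoint, so it does not bring in facility, role or sex. SAP 6.10.2.2 labels the risk difference as unadjusted but gives the hazard ratio no such label.

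**The concern.** The odds ratio and the hazard ratio describe the same outcome in the same participants, yet one is conditional on facility, role and sex and the other is not. Facilities enter after an index case, and it is plausible that some then have an outbreak and others do not, so the facility is likely to be strongly prognostic. A hazard ratio is non-collapsible: if facilities differ in hazard and the drug works, a model that pools them has a hazard ratio nearer 1 than the one within each facility.

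What is at stake is interpretation. The Cox model censors participants whose follow-up is incomplete at the event-driven lock, whereas the primary analysis counts them as event-free (SAP 6.3.2). A natural use of the hazard ratio is to ask whether that rule matters. If the two models also differ in adjustment, a gap between them cannot be put down to censoring alone.

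**Working it through.** **Inputs from the documents.** Part 1: 1:1 allocation, two-sided 0.05, 90% power, placebo 8-week rate 4.0% for moderate-or-worse COVID-19, risk ratio 0.33, 33 events (SAP 5.2). Part 2 placebo rate: 5.3%. No placebo rate is given for mild-or-worse COVID-19, the outcome of this Cox model. Because moderate-or-worse cases are a subset, that rate is at least 4.0% if the planning figure is right.

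**Assumptions (not in the documents).** SD of the log hazard between facilities, number of facilities, role and sex hazard ratios, and placebo rates of 10% and 20%.

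**Step 1: the plan's own figure.** Schoenfeld, 1:1: events = 4(1.960 + 1.282)² / (ln HR)².

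- HR 0.33: 34.2, rounded up to 35.
- HR implied by risks of 4.0% and 1.32%, ln(0.9868)/ln(0.96) = 0.3255: 33.4, rounded up to 34.
- Power with 33 events at HR 0.33: 89.0%.

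The stated 33 events are reproduced closely enough. The documents state no figure for the Cox hazard ratio itself.

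**Step 2: large-sample limit of the treatment-only Cox estimate.** Let the hazard be H₀·u on placebo and 0.33·H₀·u on drug, where u is a log-normal facility effect times role and sex effects, and time t runs from 0 to 1 over the 8 weeks. The pooled survival curves are S₀(t) = E[exp(−H₀tu)] and S₁(t) = E[exp(−0.33H₀tu)]. H₀ is set so that 1 − S₀ at 8 weeks equals the placebo rate. With event densities f₀ and f₁, the limit β solves ∫ f₁ = ∫ (f₀ + f₁)·S₁e^β / (S₀ + S₁e^β).

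Results for e^β with resident/staff HR 2 and sex HR 1.2:

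| Placebo rate | SD 0 | SD 1 | SD 1.5 |
|---|---|---|---|
| 4% | 0.331 | 0.339 | 0.357 |
| 5.3% | 0.331 | 0.341 | 0.363 |
| 10% | 0.331 | 0.350 | 0.383 |
| 20% | 0.333 | 0.367 | 0.415 |

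At 4% and SD 1.5 the shift is 0.357 − 0.330 = 0.027; at 5.3% it is 0.033. With SD 2 and role HR 3 the limit is 0.393 at 4% and 0.433 at 10%. With no treatment effect it is 1.000 (checked at a 20% rate, SD 1.5).

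**Step 3: does stratifying by facility recover 0.33?** Simulation with 1300 participants in 70 facilities, 400 trials per setting, randomized within facility, role and sex. Role HR is 2, except 1 in the first row, and there is no sex effect. Median HR, treatment-only against facility-stratified:

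| Rate, SD | Events | Treatment-only | Stratified | Power |
|---|---|---|---|---|
| 4%, 0 | 35 | 0.323 | 0.321 | 86.3% / 86.3% |
| 4%, 1 | 34 | 0.350 | 0.343 | 82.5% / 83.5% |
| 4%, 1.5 | 36 | 0.357 | 0.337 | 83.3% / 84.0% |
| 10%, 1 | 89 | 0.349 | 0.332 | 99.3% / 99.3% |
| 20%, 1.5 | 186 | 0.414 | 0.340 | 100% / 100% |

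A second simulation, with 65 facilities of 20 and SD 2, gave 0.38 against 0.33 at 4% and 0.42 against 0.33 at 10%. It found no meaningful loss of power from stratifying even with zero facility spread.

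**Step 4: scale against sampling error.** With 33 events split about 25:8, SE(ln HR) = √(1/25 + 1/8) = 0.41, so the 95% interval around 0.33 is about 0.15 to 0.73. At 4% and SD 1.5 the shift is ln(0.357/0.330) = 0.079, about one fifth of a standard error.

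**The case against.** Four points on the other side stand, and each limits what may be inferred.

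- **The treatment-only hazard ratio is not wrong.** A reader might call it biased or diluted. Under randomization it is a valid marginal quantity; the gap is non-collapsibility, and there is no false-positive inflation. The risk difference beside it is deliberately unadjusted, so a marginal hazard ratio would be a defensible choice if the SAP said so.
- **No confirmatory decision rests on it.** It sits among the additional analyses, outside the testing scheme of SAP 6.5. The primary p-value comes from the score test in the adjusted logistic model, so a loss of power here has little consequence.
- **It is not the only analysis that addresses incomplete follow-up.** A reader might infer that it is. SAP 6.3.1 and 6.3.2 plan logistic analyses weighted by the proportion of the Evaluation Period completed, and SAP 6.1.5 repeats the primary-lock analyses at the End of Evaluation lock.
- **Stratifying will not make the hazard ratio equal the odds ratio.** A risk ratio of 0.33 is an odds ratio of 0.321 at a 4% rate and 0.283 at 20%, so part of any gap belongs to the choice of measure.

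It is also fair that the SAP sentence does not itself say treatment alone; that reading needs Protocol 9.4.1 together with the SAP's silence. And at the planning rates with moderate facility spread, the shift is small beside its standard error.

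None of this removes the mismatch. The SAP never says that an unadjusted hazard ratio is intended, and the specified model ignores the groups within which participants were randomized.

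**Conclusion.** The concern holds as a mismatch of limited size in a supplementary analysis. The Cox model leaves out facility, role and sex, while the randomization, the primary model and the mixed-model sensitivity analysis all use them. Given a within-facility hazard ratio of 0.33, the treatment-only value is about 0.33 to 0.36 at placebo rates of 4 to 5.3% with facility SD up to 1.5. It reaches about 0.42 at a 10% rate with SD 2. The direction requires a real effect and prognostic strata. The size rests on an assumed facility variance and on an unstated placebo rate for mild-or-worse disease. The documents do not support a stronger conclusion that the primary result is compromised or that the hazard ratio is invalid.

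**What to change.** In SAP 6.10.2.2, fit the Cox model stratified by facility (a separate baseline hazard for each, with no facility parameters to estimate), with role and sex as covariates. Report the treatment-only hazard ratio beside it, labelled as unadjusted in the way the risk difference already is.

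The cost is one model option and a sentence of text, with no new data. Protocol 9.4 allows a change of analysis method that is not a principal feature to be described and justified in the SAP and the clinical study report, so a protocol amendment should not be needed. The small downside is that facilities with no events contribute nothing to the stratified estimate, as is already so for the treatment effect in the primary logistic model with fixed facility effects.

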#### **6.10.2.3. Fully Dosed Population**

As a sensitivity analysis, the primary and key secondary outcomes will be assessed using the Fully Dosed Population. Similar methodology, as described in Section 6.10.1 will be utilized for statistical hypothesis testing.

### ***6.10.3. Secondary Efficacy Analyses***

#### **6.10.3.1. Incidence of Moderate-or-Worse Severity COVID-19 by Day 57**

As a key secondary endpoint, the proportion of patients in the Prevention populations who develop moderate-or-worse severity COVID-19 (defined as the detection of SARS-CoV-2 by polymerase chain reaction (RT-PCR) AND moderate or worse disease severity within 21 days of detection) by Day 57 will be summarized by treatment group. Similar methodology, as described in Section 6.10.1 will be utilized for statistical hypothesis testing, following the testing scheme described in Section 6.5.

As a sensitivity assessment, participants who develop COVID-19 within 21 days of becoming SARS-CoV-2 positive by RT-PCR, then continue on to develop moderate-or-worse disease severity by Day 57, will be included as moderate-or-worse severity COVID-19 events in the assessment.

As an exploratory analysis, the incidence of moderate-or-worse severity COVID-19 within 21 days of randomization will be compared across treatment groups in the subset of participants in the Treatment populations who did not have moderate-or-worse severity COVID-19 at baseline. Statistical comparisons will use similar methodology as described in Section 6.10.1.

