The maximum total duration of study participation for each participant of the treatment group is 12 weeks. See the SOA for the treatment group in Section 1.3.2.

This table describes the visit types for the prevention population for this study.

Study Day	Activity	Visit Type
0,1	Follow SoA	Onsite
8, 15, 22, 29, 36, 43, 50, 57	Follow SoA Vital signs*	Onsite or Home (Virtual [record collection] if hospitalized)

Daily 2 - 57	Vital signs and symptoms questionnaire daily* Vital signs, clinical status, and concomitant procedures for hospitalized participants.	Onsite or Home (Virtual [record collection] if hospitalized)
ETV and follow-up (85, 141, 169)	Follow SoA	Onsite or Home

*Collected via direct data capture for onsite or home visits only.

This table describes the visit types for the treatment population for this study.

Study Day	Activity	Visit Type
0, 1	Follow SoA	Onsite
8, 29	Follow SoA Vital signs*	Onsite or Home (Virtual [record collection] if hospitalized)
Daily 2-29	Vital signs, clinical status, and concomitant procedures for hospitalized participants.	Virtual (record collection) if hospitalized
ETV and follow-up (85)	Follow SoA	Onsite or Home

*Collected via direct data capture for onsite or home visits only.

Hospitalization

If a participant is hospitalized, efforts will be made to retrieve hospital records and report procedures and assessments according to the SoA, as feasible.

Definitions for COVID-19 Severity

This table gives the definitions for COVID-19 severity of illness for those participants who are SARS-CoV-2 positive as determined by standard RT-PCR assay or equivalent test.

Table 1 Definitions for COVID-19 Severity

Severity	Description
Mild	Mild symptoms that could include: 
 fever, cough, sore throat, malaise, headache, muscle pain, gastrointestinal symptoms, without shortness of breath or dyspnea AND No clinical signs indicative of Moderate, Severe, or Critical Severity
Moderate	Symptoms of moderate illness with COVID-19, which could include any symptom of mild illness or shortness of breath with exertion AND Clinical signs suggestive of moderate illness with COVID-19, such as: 
 respiratory rate \geq 20 breaths per minute,

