8.1.2. Participant Symptoms Questionnaire

Participants will be asked about the presence or absence of symptoms and signs associated with COVID-19 experienced during the past 24 hours, at the timepoints described in the SoA.

Signs and symptoms associated with COVID-19 should not be captured as AEs, unless more severe than expected. See Section 10.3.1. for additional information AE definitions used in this study.

Symptoms include

- shortness of breath with movement
- shortness of breath at rest
- cough
- chest pain or discomfort with breathing
- feeling feverish
- chills
- sore throat
- muscle or body aches and pain
- fatigue or loss of energy
- headache
- nausea
- diarrhea
- vomiting
- loss of appetite
- loss of taste, and
- loss of smell.

Participants requiring a legally authorized representative to provide signed informed consent will not be asked to report the presence or absence of symptoms. Only symptoms that may be observed by site staff other than the participant will be recorded, including

- shortness of breath with movement
- shortness of breath at rest
- cough
- diarrhea, and
- vomiting.

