#### 6.1.1. Analysis Populations

Patient populations are defined in [Table PYAD.6.1](#) along with the analysis they will be used to conduct. The treatment groups and inferential comparisons described in [Table PYAD.6.1](#) will be used unless otherwise specified. Also, unless otherwise specified, for all populations/analysis, patients will be analyzed according to the treatment to which they were assigned.

If enrolling to a placebo-controlled trial is challenged by an effective medication becoming available for prevention of COVID-19 and SARS-CoV-2, then the placebo arm may be dropped in Part 2.

Throughout the document, the term “the Prevention populations” will be used to describe both the Part 1 Prevention and Part 2 Prevention populations. Analyses on the Prevention populations will be conducted on each Prevention population separately. The terms “the Treatment populations” and “the Safety populations” are defined similarly, including those populations from Part 3 of the study.

Table PYAD.6.1. Analysis Populations

Population	Description
Entered	
Definition: All patients who signed informed consent.
 
Purpose: Used for disposition analysis.
 
Treatment Groups: None
 
Inferential Comparisons: None

Enrolled/Intent-to-Treat (ITT)	
Definition: All participants assigned to treatment, regardless of whether they take any doses of study treatment, or if they took the correct treatment. Patients will be analyzed according to the treatment group to which they were assigned.
 
Purpose: Used for disposition, demographic, and safety analyses.
 
Treatment Groups (Short Label):
 
 
Part 1: 4200 mg LY3819253 (4200 LY) and placebo (Pbo)
 
Part 2: 700 mg LY3819253, 350 mg LY3819253 + 700mg LY3832479, and placebo
 
 
Inferential Comparisons: LY versus placebo

Part 1 Prevention	
Definition: All participants in the Enrolled/Intent-to-Treat population in Part 1 who are SARS-CoV-2 RT-PCR negative and serology negative at baseline.
 
Purpose: Used for efficacy and health outcomes analyses.
 
Treatment Groups (Short Label): 4200 mg LY3819253 (4200 LY) and placebo (Pbo)
 
Inferential Comparisons: LY versus placebo

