### ***6.3.2. Missing COVID-19 Status or Disease Severity***

For the primary and key secondary endpoints, if a participant has at least one post-baseline RT-PCR test result and has not yet met the criterial for COVID-19 or is missing data used to determine COVID-19 status, the participant will be treated as not experiencing COVID-19. The same logic will be used for moderate-or-worse severity COVID-19.

As a supplementary analysis on these endpoints, the approach described in Section [6.3.1](#) will be used to handle missing COVID-19 status or disease severity due to death unrelated to COVID-19, study discontinuation, or the triggering of the Primary Database Lock. Participants with missing information will be treated as not experiencing the associated endpoint event and will be weighted based on the proportion of the Evaluation Period that was completed.

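### SAP 6.10.3.1 extends an exploratory 21-day severity comparison to Part 2 Treatment and Part 3, whose schedule cannot reliably classify non-hospitalized cases

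*SAP*

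**What the plan says.** - **Planned comparison, moderate or worse.** SAP 6.10.3.1 compares 21-day incidence between arms "in the subset of participants in the Treatment populations who did not have moderate-or-worse severity COVID-19 at baseline", labels this exploratory, and refers back to 6.10.1 for method.
- **Who is covered.** SAP 6.1.1 states that the plural terms for the Treatment and Safety populations "are defined similarly, including those populations from Part 3 of the study".
- **Planned comparison, mild or worse.** SAP 6.10.1 has a matching exploratory analysis "in the subset of participants in the Treatment population who are asymptomatic at baseline". It uses the singular and names no Part.
- **Severity definition.** Protocol Table 1 requires symptoms and clinical signs for Moderate and for Severe. Mild rests on symptoms without signs of a worse grade. Critical and Death do not depend on reported symptoms.
- **Data collection.** Protocol 1.3.1 (Part 1 and Part 2 Prevention) has a daily symptoms questionnaire, a daily row for clinical symptoms and interventions, and daily vital signs. Protocol 1.3.2 (Part 2 Treatment and Part 3) has neither symptom row, and its evaluation visits are Days 1, 8 and 29. For the treatment population, the daily Day 2 to 29 entry in the protocol 4.1.2 visit table is "Vital signs, clinical status, and concomitant procedures for hospitalized participants", gathered from records.
- **Adverse event forms.** Protocol 8.1.2: "Signs and symptoms associated with COVID-19 should not be captured as AEs, unless more severe than expected".
- **Missing severity.** SAP 6.3.2, scoped to the primary and key secondary endpoints, provides that if someone "is missing data used to determine COVID-19 status, the participant will be treated as not experiencing COVID-19", and extends this to moderate-or-worse disease. SAP 6.3.3 applies non-responder imputation to other categorical efficacy endpoints and counts anyone not adequately assessed as a treatment failure.

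**The concern.** An incidence analysis needs its event to be observable in every participant analysed. In Part 1 the 21-day severity events can be built from daily symptoms and vital signs. In Part 2 Treatment and Part 3, symptoms of participants who stay out of hospital are not systematically recorded after baseline, and signs are scheduled once in the window. The SAP nevertheless prespecifies the same between-arm comparison there.

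At stake is a comparison of monotherapy with the combination in people already infected. If run as written, its result would reflect which cases happened to be detected and which missing-data rule the analyst picked, more than the course of illness. Part 3 is open label, so leaving that choice until data have accrued is a further weakness.

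**Working it through.** The documents give no event count, power or expected rate for this comparison, so there is no planned figure to reproduce. The check sets the texts side by side and then counts days.

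**1. Where the documents place 21-day severity incidence**

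| Source | Part 1 Treatment | Part 2 Treatment | Part 3 |
|---|---|---|---|
| Protocol Section 3 endpoint lists | yes | no | no |
| SAP Tables 4.4, 4.5, 4.6 | yes | no | no |
| SAP 6.16.1.1 (time to improvement, also severity-based) | yes | no | no |
| SAP 6.10.3.1 read with 6.1.1 | yes | yes | yes |

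The last row is out of line with the others.

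**2. What each schedule collects after dosing, outside hospital**

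| Item | Protocol 1.3.1 | Protocol 1.3.2 |
|---|---|---|
| Symptoms questionnaire | daily | none |
| Clinical symptoms and interventions row | daily | none |
| Vital signs, Days 2 to 21 | daily: 21 − 2 + 1 = 20 days | 1 planned day (Day 8) |
| Symptom-directed examination | as indicated | as indicated |

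**3. The window.** Twenty-one days end on Day 21 if Day 1 counts as the first day, or on Day 22 if it does not. The Day 8 visit may fall on Days 7 to 9. The Day 29 visit may fall on Days 27 to 31; its earliest date, Day 27, is outside the window either way. Days left with no planned outpatient visit:
- after the latest Day 8 visit (Day 9): 21 − 9 = 12, or 22 − 9 = 13;
- after a nominal Day 8 visit: 21 − 8 = 13, or 22 − 8 = 14.

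**4. The two missing-data rules.** Let *h* be the share of an arm with a detected event and *u* the share without one who are judged not adequately assessed.
- Rule as in SAP 6.3.2 (missing is no event): estimated incidence = *h*, which is limited to hospitalized and incidentally detected cases.
- Rule as in SAP 6.3.3 (not assessed is failure): estimated incidence = *h* + *u*. If everyone without a detected event is judged not adequately assessed, *u* = 1 − *h*. Incidence is then 100% in both arms and the difference is zero whatever the treatments do.

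The reference in 6.10.3.1 to the methods of 6.10.1 does not choose between them, because 6.10.1 sets out a regression model and no missing-data rule.

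**5. Illustration of under-capture, on assumed rates only.** Take the Part 3 ceiling of about 500, so 250 per arm, two-sided 0.05, and the same captured fraction *c* in both arms. Power = Φ[(Δ − 1.96·SE₀)/SE₁], with Δ the difference in captured rates, SE₀ the pooled and SE₁ the unpooled standard error. For 20% versus 10% with full capture: Δ = 0.10, SE₀ = 0.0319, SE₁ = 0.0316, so (0.10 − 0.0626)/0.0316 = 1.18 and power is 0.882.

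| Assumed true rates | *c* = 1 | *c* = 0.5 | *c* = 0.25 |
|---|---|---|---|
| 10% vs 5% | 0.565 | 0.312 | 0.176 |
| 20% vs 10% | 0.882 | 0.565 | 0.312 |
| 30% vs 15% | 0.982 | 0.758 | 0.444 |

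For 20% versus 10%, the risk difference falls from 10 to 5 to 2.5 points while the risk ratio stays at 0.5. This describes the first rule in step 4 only. The documents do not give the captured fraction.

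**The case against.** The best defence is that the plural in 6.10.3.1 is a slip. Every endpoint list confines these outcomes to Part 1 Treatment, protocol 9.4.7 makes repeats in the Treatment populations optional, and 6.10.1 uses the singular. The analysis is exploratory, sits outside the alpha-controlled tests, and Part 3 is declared not powered for inference. All of that stands. It supports a wording correction but does not make the text as written workable, because 6.1.1 defines the plural explicitly.

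Several stronger readings are tempting and should not be adopted:
- **That outpatient cases will be scored as non-events**, giving near-zero incidence and an appearance of equal, high protection. SAP 6.3.2 does not cover exploratory endpoints, and 6.3.3 points the opposite way. The direction of bias is not established.
- **That no symptoms are collected.** Symptom-onset timing is taken with the history and an examination is allowed as indicated. Day 8 vital signs supply the signs, and can show fever on that day. Hospital and emergency room events are recorded. Structured collection after baseline is what is absent.
- **That baseline asymptomatic status cannot be set from the questionnaire in either part.** Part 2 screening follows protocol 1.3.1, which includes the questionnaire. The point applies to Part 3 only, and there the history and inclusion criterion 20 still separate symptomatic from asymptomatic participants.
- **That about 500 participants are affected.** That is the Part 3 enrolment ceiling and the floor is 30. The analysis set is smaller again, being RT-PCR positive, serology negative and restricted on baseline severity.

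Part 1 is not a perfect comparator either: where a representative gives consent, only five observable symptoms are recorded.

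**Conclusion.** The point holds in limited form. Read with its own definition, SAP 6.10.3.1 commits to a 21-day moderate-or-worse comparison in Part 2 Treatment and Part 3, and non-hospitalized Mild, Moderate or Severe illness cannot be classified reliably there. There is one planned post-baseline visit in the window, and at least 12 days after the latest permitted date for it have no planned outpatient contact. Scoring of the resulting gaps is unsettled between two opposite rules, and the comparison is uninterpretable under both. For the mild-or-worse analysis in 6.10.1 the defect is ambiguity about which Part is meant.

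The conclusion rests on the schedules as written and assumes no unscheduled source fills the symptom gap systematically. No primary or key secondary conclusion changes. The matter is worth correcting because the comparison is prespecified and the correction is simple.

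**What to change.** In SAP 6.10.1 and 6.10.3.1, have the 21-day severity analyses name the Part 1 Treatment population alone. This agrees with protocol Section 3, SAP Tables 4.4 to 4.6 and SAP 6.16.1.1.

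For Part 2 Treatment and Part 3, rely on the protocol-listed endpoints over the 4-week evaluation period: hospitalization or death, emergency room visits, COVID-19 mortality, worst NIAID score and virology. SAP 6.10.3.4 to 6.10.3.6 already repeat the hospitalization-or-death, deterioration and mortality analyses in the Treatment populations, so little new text is needed.

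The cost is SAP wording, with no change to data collection, and the loss of one exploratory comparison that the collected data cannot support. If the sponsor wants to keep it in Parts 2 and 3, the SAP should state which recorded data define each severity grade there and which missing-data rule applies.
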